3.4.1 Group sequential design with 2 interim analyses

The planned sample size is a minimum of 254 and a maximum of 508 subjects.

The sample sizes for this trial are calculated using the following assumptions:

- significance level equal to 0.025 (1-sided)
- power of 0.8 (at final analysis)
- allocation ratio of 1:1
- Two interim analyses at half and three-quarter information time (i.e. when half and three-quarter of the subjects are evaluable for response), using spending functions with O'Brien-Fleming-Type boundaries for efficacy and futility.
- Efficacy endpoint (%All in optimal, more is better) on logit-scale:
 - Mean conventional = -1.86
 - Mean INTELLiVENT-ASV = -1.28
 - \circ Sd = 1.5 for both devices
- Safety endpoint (%Any in sub-optimal, less is better) on logit-scale:
 - Mean conventional = -0.09
 - Mean INTELLiVENT-ASV = -0.74
 - \circ Sd = 1.6 for both devices
- Correlation between endpoints = -0.85
- Dropout could occur when subjects are ventilated for less than 24 hours after inclusion because of unexpected death, transfer to another ICU or withdrawal of informed consent. A maximum dropout rate of 5% of these cases is expected. Given the large uncertainty on the assumed performance differences and the inclusion of a sample size reassessment, the initial sample size is not increased to deal with this dropout rate. At the second interim the sample size will be re-estimated, taking this observed dropout rate into account.

The table below shows the sample sizes and characteristics of a study with 2 interim analyses, with O'Brien-Flemming boundaries for efficacy and futility. The final sample size for this group sequential design is 254. 254 stands for the number of subjects with evaluable endpoints and means more subjects might have to be enrolled to reach this number. The p-values for significance are increasing at each analysis while the p-value to stop for futility decreases from the first interim analysis to the final analysis. The study has a high probability to stop at the first interim analysis if both ventilation modes have an equal performance.

Sample sizes and operational characteristics for the trial using O'Brien Fleming boundaries for futility and efficacy.

Analysis	SS	Z	Nominal p	α Spend	end Power	
		Efficacy	Efficacy		(Prob stop H _A)	
1 (IA1)	128	2.96	0.0015	0.0015	0.25	

2 (IA2)	192	2.36	0.0093	0.0097	0.
3 (final)	254	2.02	0.0220	0.0250	0
Analysis	SS	Z	Nominal p	Prob Futility Stop	
		Futility	Futility	(Prob stop under H ₀)	

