4.3.1 Intention-To-Treat (ITT) Population

The Intention-To-Treat population (ITT) will consist of all randomized subjects. Subjects who receive the wrong ventilation support will be analysed in the arm to which they were randomized. The ITT population will be used for primary, secondary, and tertiary efficacy analyses.

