4.8 Methods to be used for handling Missing Data

The subject dataset is considered complete if both of the following conditions are met:

- 1. Minimum of 24h of recorded data available
- 2. Minimum of 80% of the total invasive ventilation time within the allocated randomized ventilation mode has been recorded.

An incomplete dataset leading to a dropout in the study is a dataset that misses at least one of the above-mentioned variables. Subjects for which less than 80% of mechanical ventilation time within the allocated randomized ventilation mode could be recorded due to documented technical reasons, the recorded data (with 'percent spent' calculated per

the recorded time) will be used for the primary analysis of the co-primary endpoints. A maximum of 5% of subjects with less than 80% recorded time is expected. As a sensitivity analysis, these values will be treated as missing data and imputed as described below.

Method that takes into account the presence of missing data and that yield valid estimates under the assumption of data missing at random (MAR) will be used. For the primary analysis, multiple imputation of the missing primary outcome data in both arms will be performed under a missing at random model for the control arm, hence leading to a conservative imputation. The 'percent spent' variables that need to be imputed are continuous-type variables. Those variables will be imputed sequentially using covariates constructed from the corresponding sets of preceding variables, in this case. In addition, should there be any issues with the estimation of the model, the covariates will be prioritized based on the order in which they are listed below.

- Study arm
- Demographic data: Age and gender at Baseline (visit 2)
- Pulmonary condition at visit 1
- History: Cause of ICU admission and patient medical history at baseline (visit 2)
- Intubation status at Visit 5
- ICU severity scores: SAPS II, APACHE and SOFA at visit 5
- Concomitant rescue therapies: Proning, Nitric Oxide at visit 5
- Weaning Information: Active/Passive, NIV, CPAP, weaning process and sedation status at visit 5

Multiple imputation will be used in secondary, tertiary or sensitivity analyses, whenever necessary, to impute the missing data under the MAR assumption.

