7.3 Tertiary Efficacy Variable

The tertiary efficacy endpoint is a composite endpoint and will be used to assess the ability to keep ventilation and oxygenation variables in optimal target ranges. The tertiary efficacy variable will be calculated as the percentage of time spent with **ALL** six variables in the optimal target ranges during the ventilation period **from day 8 up to day 28** after randomization:

- 1) Tidal volume (VT)
- 2) Maximum pressure (Pmax)
- 3) Oxygen saturation measured by pulse oximetry (SpO₂)
- 4) End-tidal partial pressure of carbon dioxide (PetCO₂)

- 5) Respiratory rate (RR) for spontaneous breathing subjects
- 6) Pmax-PEEP for passive ARDS subjects

The optimal and sub-optimal ranges are defined by pertinent guidelines for different clinical conditions including normal lungs, brain injury, ARDS, and chronic hypercapnia.

The tertiary efficacy variable will be expressed by median (interquartile range). Log transformation will be performed on the data before performing the 2 sample Z-test. Comparisons will use the 2 sample Z-test for log transformed variables. The P values <0.025 (one-sided, the hypothesis is that INTELLiVENT-ASV is better than conventional non-automated ventilation in terms of efficacy) will be considered significant.

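### The Day 8-28 tertiary percentages are undefined for subjects no longer ventilated, yet the SAP tests them at one-sided p<0.025, sets no rule for such subjects, and does not bar imputing them

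*SAP*

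**What the plan says.** **Measure.** SAP 3.2.3, 7.3 and 8.4 define the tertiary variables as the percentage of time with all six variables optimal (efficacy), or at least one sub-optimal (safety), while the subject is being ventilated between Day 8 and Day 28.

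**Populations.** SAP 4.3.1 defines ITT as everyone randomized and says: "The ITT population will be used for primary, secondary, and tertiary efficacy analyses". Protocol 10.4.2 had named ITT for primary efficacy only. SAP 8.4 puts tertiary safety in the Safety population, meaning everyone who ever received invasive mechanical ventilation. SAP 10.1 also lists tertiary efficacy in the MITT population.

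**Missing data.** SAP 4.8: "Multiple imputation will be used in secondary, tertiary or sensitivity analyses, whenever necessary, to impute the missing data under the MAR assumption". The covariates listed for imputation stop at Visit 5, which SAP Appendix 1 places on Day 1. The missing-not-at-random checks in SAP 7.4 cover primary efficacy only.

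**Test.** SAP 7.3 uses a two-sample Z-test on log-transformed data. One-sided p<0.025 for the hypothesis that the device is "better than conventional non-automated ventilation in terms of efficacy) will be considered significant". SAP 8.4 repeats this for tertiary safety. SAP section 4 mentions Bonferroni adjustment only where applicable.

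Neither document says what happens, in these analyses, to a subject with no ventilation after Day 7.

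**The concern.** A percentage of ventilated time needs ventilated time as its denominator. Someone extubated on Day 4, or dead on Day 5, has none in the Day 8-28 window. Nothing was lost; there was nothing to record. A missing-at-random model presumes that a true value exists and was not seen. Applied here, it would create values for ventilation that never took place, from covariates no later than Day 1.

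The alternative is to analyse only subjects still ventilated. Weaning and survival after randomization then decide who is in the comparison, and the device may influence both. Weaning differs by arm: an automated weaning function with automatic breathing trials in the device arm (Protocol 8.3.3), and a clinician-run weaning trial in control (Protocol 8.3.2). Protocol 9.1 expects mortality of around 30%. The two remaining groups need not be comparable, and a p-value does not change that.

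At stake is whether a pivotal trial meant to support a pre-market application can label a Day 8-28 result significant. Two analysts could both follow this SAP and report tertiary efficacy on about 50 subjects or on 254.

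**Working it through.** **1. The plan's own figure.** No sample size, power or expected number evaluable is given for the tertiary endpoints. The only design figure is 254 evaluable subjects for the co-primary endpoints (SAP 3.4.1), from these inputs:
- "significance level equal to 0.025 (1-sided"), "power of 0.8 (at final analysis") and "allocation ratio of 1:1".
- Efficacy on the logit scale: "Mean conventional = -1.86" and "Mean INTELLiVENT-ASV = -1.28", a difference of 0.58, with SD 1.5.
- Safety: -0.09 against -0.74, a difference of 0.65, with SD 1.6. The correlation between endpoints is -0.85.

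Fixed designs need 210 (efficacy) and 192 (safety) subjects in total. Simulating 2 million trials with looks at 128/192/254, efficacy bounds 2.96/2.36/2.02 and futility bounds 0.44/1.34/2.02 gives joint power of 0.801, against the stated 0.80. The co-primary design reproduces.

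**2. Duration figures in the documents.**
- Annex A Table 10: 2-8 days of mechanical ventilation, not labelled as range, interquartile range or means.
- Annex B Table 13, observational device cohort: 9400 h / 100 subjects / 24 = 3.9 days.
- Annex B Table 13, earlier device trial counting manual setting changes: 3168 h / 30 / 24 = 4.4 days. Annex A Table 12 gives 4320 h for that trial, so 4320 / 30 / 24 = 6.0 days.
- Inclusion criterion 4 (Protocol 7.2): at least 24 h of further ventilation expected.

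**3. Share still ventilated after Day 7.** The distribution shapes are my assumption, and duration T is counted from enrolment. For an exponential with mean m, P(T>7) = exp(-7/m), and given T>1 it is exp(-6/m). With median M, the formulas are 0.5^(7/M) and 0.5^(6/M). For 2-8 days as a lognormal interquartile range, the log-mean is ln 4 and the log-SD is (ln 8 - ln 2)/(2 × 0.6745) = 1.028. Counts use unrounded values.

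| Assumption | P(T>7) | of 254 | P(T>7 given T>1) | of 254 |
|---|---|---|---|---|
| Exponential, mean 3.9 | 0.167 | 43 | 0.216 | 55 |
| Exponential, mean 4.4 | 0.204 | 52 | 0.256 | 65 |
| Exponential, mean 6.0 | 0.311 | 79 | 0.368 | 93 |
| Exponential, mean 8 | 0.417 | 106 | 0.472 | 120 |
| Lognormal, IQR 2-8 | 0.293 | 74 | 0.322 | 82 |
| Exponential, median 8 | 0.545 | 138 | 0.595 | 151 |

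The first five rows span 17-47% with a value, so 53-83% without. A mean of 2 days would give 0.030 (8 subjects) or 0.050 (13); I leave it out of the range because the device studies average about twice that or more. A median of 6 days given T>1 gives exactly 0.500.

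**4. What a test on the remaining subjects could show.** I borrow the primary effect sizes as an assumption. One-sided power is Φ(δ / (σ√(2/n)) - 1.96), with n per arm:
- 17% of 254, n = 21.6: efficacy 0.245, safety 0.266.
- 47% of 254, n = 59.7: efficacy 0.561, safety 0.602.

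**5. Multiplicity.** Two tests at 0.025 carry a one-sided family-wise error of 1 - 0.975² = 0.049 if independent, and less if correlated. SAP 10.1 also marks the tertiary efficacy tables for both interim analyses, with no tertiary boundary stated.

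**The case against.** The best defence is that the SAP never says extubated or dead subjects will be imputed. Imputation is for missing data and only when needed. SAP 4.8 calls a dataset complete when at least 24 h and at least 80% of invasive ventilation time have been recorded. A fully recorded subject extubated on Day 4 meets both conditions. Listing 16.02.03 also foresees exclusions from efficacy analysis. Read together, these places fit an analysis of subjects still ventilated. This stands: the defect is a rule left open, not a stated decision to impute.

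It does not rescue the significance rule, because that reading leads to the comparison selected after randomization.

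Second, these endpoints are tertiary. Alpha and power are built on the co-primaries, and no decision or stopping rule depends on a tertiary p-value. That limits the consequence and makes multiplicity the lesser part of the point, but SAP 7.3 and 8.4 still declare significance in terms.

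Third, properly combined multiple imputation carries between-imputation variance, so imputing many values does not by itself manufacture significance. That is correct. The objection here is that the imputed quantity does not exist.

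Fourth, restricting to subjects still ventilated keeps the selection. That is also correct, so the restriction is useful only together with descriptive reporting.

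**Conclusion.** The point holds. The tertiary percentages are undefined for subjects off the ventilator by Day 8, the SAP has no rule for them, and calling p<0.025 significant is unsupported whether they are imputed or left out. Under the assumptions above, 43-120 of 254 subjects would have a value and 53-83% would not.

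Three stronger readings are tempting, and the documents do not support them:
- A reader might infer that both tertiary endpoints are tested in ITT. Only tertiary efficacy is. The Safety population does, however, also include subjects off the ventilator by Day 8.
- A reader might infer that most ITT values will be imputed. The SAP permits this without ordering it.
- A reader might take it as given that most subjects will be extubated or dead by Day 8. That is an inference from an unlabelled 2-8 day figure and two earlier device studies. With 8 days as a median, 54.5-59.5% would still be ventilated; even then, 40.5-45.5% would have no value.

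The co-primary analyses, sample size and interim rules are unaffected.

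**What to change.** Amend the SAP as follows:
- Define the tertiary analysis set, for efficacy and safety, as subjects with invasive ventilation after Day 7.
- State in 4.8 that extubation or death before Day 8 is not imputed, and report both counts by arm.
- Reserve multiple imputation in the tertiary analyses for recording failures in subjects actually ventilated in the window.
- Report estimates with confidence intervals as descriptive, with a note that the groups are selected after randomization.
- Delete from 7.3 and 8.4 the statement that p<0.025 is significant.

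The cost is SAP wording. The downside is that the trial makes no formal tertiary claim.

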If plateau pressure exceeds 35 cmH₂O or driving pressure exceeds 15 cmH₂O, tidal volume will be decreased by 1 mL/Kg IBW keeping it above 4 mL/Kg or inspiratory pressure will be decreased by 2 cmH₂O.

iii. Additional and rescue procedures:

Continuous myorelaxant infusion, repeated recruitment maneuvers, nitric oxide, and prone position will be considered as additional procedures at the clinician's discretion.

If PaO₂ ≥ 55 mmHg or SpO₂ ≥ 88% with FIO₂ of 1.0 cannot be maintained, clinicians may employ rescue procedures. APRV, high frequency ventilation, ECCO2R and ECMO will be considered as a rescue therapies. The subjects will continue to be followed and included in the analysis on an intention-to-treat basis. Failure of the protocol and subsequent need for rescue therapy will constitute a secondary outcome. Control group subjects will not be allowed to cross-over to the INTELLiVENT-ASV group.

C. Spontaneous breathing subjects:

i. Ventilator settings:

Ventilation support will be adjusted to keep tidal volume in the range:

- 6-10 mL/Kg IBW for normal lung subjects, brain injury, and COPD subjects

- 4-8 mL/Kg IBW for ARDS

Ventilation support will be adjusted to keep respiratory rate \leq 35 Breaths/min.

Inspiratory trigger settings will be set between 1 and 5 L/min or 0.5 and 2 cmH₂O or activate Intellisync+.

Expiratory trigger setting will be set between 10 and 80% of the maximal inspiratory flow or activate Intellisync+.

Pressure rise time will be set between 0 and 400 ms.

Automated tube compensation if appropriate.

D. Weaning:

The INTELLiVENT-ASV or control arm ventilator protocols will be continued until subjects are able to breathe unassisted for 48 hours, death, ICU discharge, study withdrawal, if the site's principal investigator determines that the study is no longer in the subject's best interest or day 28, whichever comes first.

i. Screening of readiness to wean criteria

A screening of readiness to wean criteria will be performed twice a day between 6h00 and 18h00 for all subjects mechanically ventilated for more than 24h.

ii. Extubation

After a successful weaning trial, extubation criteria will be assessed:

- Coma Glasgow Score > 8
- Ability to cough
- Ability to swallow
- Absence of severe upper airway obstruction
- Successful cuff leak test

If all these criteria are fulfilled, subject will be extubated within 12 hours after the successful weaning trial.

iii. Ventilation management after extubation

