9.1.2 Adverse Events (AEs)

ISO 14155 / MDR 2017/745 Definition (regulatory definition):

An AE is any untoward medical occurrence, unintended disease or injury or any untoward clinical signs, (including an abnormal laboratory finding,) in subjects, users or other persons, in the context of a clinica investigation, whether or not related to the investigational medical device. and whether anticipated or unanticipated.

NOTE 1 to entry: This definition includes events related to the investigational medical device or the comparator.

NOTE 2 to entry: This definition includes events related to the procedures involved.

NOTE 3 to entry: For users or other persons, this definition is restricted to events related to investigational medical devices.

Specificities to EASiVENT:

The following Adverse Events (**AEs**) **will be recorded during** the EASiVENT Study Days 0 through 28:

1. Serious Adverse Events (SAEs) other than those listed as study-specific outcomes
2. Non-serious AEs that are considered by the investigator to be possibly, probably, or definitely (causally) related to mechanical ventilation as a supportive measure for acute respiratory failure.
For details please refer to EASiVENT Study list of Adverse Event, [Annex D](#)
3. AEs that lead to permanent discontinuation of INTELLiVENT-ASV-Management.

Investigators will be instructed to record their assessment of the potential relatedness of each Adverse Event (AE) to protocol procedures and mechanical ventilation. Potential relatedness of an event to mechanical ventilation will be determined by evaluating the temporal relationship and if the event is unanticipated or unexplained given the patient's clinical course, care, and previous medical conditions. The degree of certainty the investigator has regarding relatedness of the event to mechanical ventilation will be recorded as not related, possibly related, probably related, or definitely (causal) related. If patient's INTELLiVENT-ASV-Management is discontinued as a result of an AE, study site personnel will clearly record in the eCRF of the Study the circumstances and data leading to discontinuation of INTELLiVENT-ASV as ventilation mode.

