12.1 Supply of investigational devices/products

Hamilton Medical investigational devices/products will be ordered and shipped to the site prior site activation as applicable. All devices are supplied with INTELLIVENT-ASV Software accessory.

However, the activation of the INTELLIVENT-ASV software accessory can be done only with a key code provided by the sponsor.

US only: The investigational device (INTELLIVENT-ASV accessory is activated), the instructions for use, or the packaging, or the ventilator will indicate that the investigational device is exclusively for use in a clinical investigation.

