4.3.3 Safety Analysis Population

The Safety population will include all subjects who once received invasive mechanical ventilation. Subjects will be analyzed according to the ventilation mode that they received. The safety population will be used for safety analyses.

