4.5 Treatment Assignment and Treatment Arms

The two ventilation arms are:

- Automated ventilation arm: INTELLiVENT-ASV software accessory will be activated, utilizing a Hamilton-Medical Ventilator
- Non automated ventilation arm: INTELLiVENT-ASV software accessory won't be activated

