Missing AE intensities will not be imputed. Such AEs will be included in summaries by including a category of "missing" in the tables. If the assessment of the relationship of the AE to investigational device is missing, we will assume that the AE is possibly related to investigational device.

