8.5 Adverse Events and Serious Adverse Events

Adverse events (AEs) will be coded using the IMDRF terminologies for categorized Adverse Event Reporting (Version 5.0) and will be graded according to the National Center Institute Common Terminology Criteria for AEs (NCI-CTCAE criteria [v5.0]). Adverse events will be analyzed in terms of their type, incidence, severity, and relationship to the study treatment.

Related AEs are defined as events with a relationship to mechanical ventilation, study procedure and INTELLiVENT-ASV equal to 'Not related', 'Related'.

A summary table will present by treatment arm the number and percentage of subjects with at least one of the adverse events, adverse device effects or observed device deficiencies.

The following tabulations will be presented:

Non-Device-Related:

- Adverse Event (AE)
- Serious Adverse Event (SAE)

Device/Procedure-Related:

- Adverse Device Effect (ADE)
- Serious Adverse Effect (SADE)
- Anticipated SADE (ASADE)
- Unanticipated Serious Adverse Device Effect (USADE)

For detailed categorization of Adverse Events, refer to protocol section 9 safety and ANNEX A in the protocol.

Listings of all adverse events by treatment arms will be provided, flagging the ones that are Device/Procedure-Related.

The relationship between the use of the medical device (including the medical - procedure, i.e., invasive mechanical ventilation) and the occurrence of each adverse event will be assessed and categorized.

Each SAE will be classified according to four different levels of causality.

- 1. Not related to the device in question
- 2. Possible
- 3. Probable
- 4. Causal relationship

A frequency table will be provided to assess the relationship of the serious adverse event to INTELLiVENT-ASV.

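### The SAP's rule for a missing device-relationship rating is not limited to subjects exposed to INTELLiVENT-ASV, so unexposed controls can be labelled possibly device-related in the descriptive safety outputs

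*SAP*

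**What the plan says.** - **The rule.** SAP 4.8 states that if "the assessment of the relationship of the AE to investigational device is missing, we will assume that the AE is possibly related" to that device. It names no arm and no exposure condition.
- **The device.** Protocol 12.1, in its US labelling text, identifies it by activation of the software: "The investigational device (INTELLIVENT-ASV accessory is activated".
- **Control exposure.** SAP 4.5 has "Non automated ventilation arm: INTELLiVENT-ASV software accessory won't be activated", and Protocol 8.3.1 adds "Control group subjects will not be allowed to cross-over to the INTELLiVENT-ASV group".
- **Safety set.** SAP 4.3.3: "Subjects will be analyzed according to the ventilation mode that they received".
- **What is rated.** Protocol 9.1.2 tells investigators to "record their assessment of the potential relatedness of each Adverse Event (AE) to protocol procedures and mechanical ventilation". INTELLiVENT-ASV is not named there, for either arm. SAP 8.5 lists it as a third target beside mechanical ventilation and study procedure.
- **Where the rating goes.** SAP 4 says tables are made by arm. SAP 8.5 says "A summary table will present by treatment arm the number and percentage of subjects with at least one of the adverse events", and extends this to adverse device effects and device deficiencies. It also plans ADE, SADE, ASADE and USADE tabulations and a frequency table of SAE relationship to INTELLiVENT-ASV.

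**The concern.** Treating an unknown relationship as possible is a conservative convention where the subject was exposed: it can only add to the device's count. In a control who never received INTELLiVENT-ASV nothing is unknown. A blank means either that nobody answered or that the question did not apply, and in both cases a relationship to that device is impossible. A programmer following SAP 4.8 literally would still write possibly related for that event.

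The most informative pattern in a device-relatedness table is events in one arm and none in the other. False control entries remove it. The Protocol synopsis presents the trial as the primary basis for a pre-market application and the benefit-risk determination, so the device-relatedness tables should not contain entries known to be wrong.

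**Working it through.** The documents give no expected rate of missing ratings and no figure that depends on this rule, so there is nothing to reproduce. The check has two parts.

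**1. What the rule does to an unexposed control.** No activation (SAP 4.5), no cross-over (Protocol 8.3.1) and analysis by mode received (SAP 4.3.3) together mean that a subject counted as control in the safety set normally had no INTELLiVENT-ASV exposure. The true device relationship is none; SAP 4.8 yields possibly related. That the rule reaches both arms is inferred from the absence of a restriction. The SAP does not say so in words.

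**2. Size.** One adverse event per subject, missingness unrelated to true relatedness, and the same AE share in both arms. All rates below are assumptions.

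- q = share of subjects with an AE
- p = true device-related share in the INTELLiVENT arm (control: 0)
- mT, mC = share of ratings missing in the INTELLiVENT and control arms
- Counted in INTELLiVENT arm = p + mT(q - p)
- Counted in control arm = mC × q
- If mT = mC = m, the difference is p + m(q - p) - mq = p(1 - m)

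| q | p | mT | mC | INTELLiVENT | Control | Difference |
|---|---|---|---|---|---|---|
| 40% | 5% | 0 | 0 | 5.0% | 0% | 5.0 |
| 40% | 5% | 5% | 5% | 5 + 0.05×35 = 6.75% | 0.05×40 = 2.0% | 4.75 |
| 40% | 5% | 20% | 20% | 5 + 0.20×35 = 12.0% | 0.20×40 = 8.0% | 4.0 |
| 20% | 10% | 5% | 50% | 10 + 0.05×10 = 10.5% | 0.50×20 = 10.0% | 0.5 |
| 20% | 10% | 5% | 100% | 10.5% | 1.00×20 = 20.0% | -9.5 |

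With equal missingness the absolute difference barely moves, but the counts blur more. At 127 per arm (254 in SAP 3.4.1, split 1:1), the 20% row is 0.12×127 = 15.2 against 0.08×127 = 10.2 subjects, where the truth is 0.05×127 = 6.4 against 0.

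Setting the two counts equal gives the control missingness beyond which the sign reverses: mC = mT + (p/q)(1 - mT). With mT = 5%:

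- p/q = 10/20: 0.05 + 0.50×0.95 = 52.5%
- p/q = 5/40: 0.05 + 0.125×0.95 = 16.9%
- p/q = 2%: 0.05 + 0.02×0.95 = 6.9%

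The threshold always exceeds mT when p is above zero, so equal missingness cannot reverse the sign under these assumptions. The margin is narrow when few events are truly device-related.

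**After the fix**, with q = 40%, p = 5% and mT = 5%, the table shows 6.75% against 0%. It overstates the true 5 points, which is the direction the rule intends.

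**The case against.** The strongest opposing case is that this is a wording matter in tables that carry no inference. Much of it stands.

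- **Endpoints.** Primary safety is time with at least one variable sub-optimal (SAP 8.2). Secondary safety counts all SAEs, plus rescue therapy (SAP 8.3). Neither uses the device rating. SAP 8.5 states no between-arm test of related events. A reader might infer that the trial's safety conclusion rests on this rule; it does not.
- **Control entries are not all false.** The ADE definition in Protocol 9.2.2 includes a comparator that is a medical device, controls are on Hamilton ventilators, and SAP 8.5 groups device with procedure. Genuine control entries can appear in those rows. The zero true rate applies only to relationship to INTELLiVENT-ASV itself, and SAP 8.5 does not say whether its SAE frequency table includes controls.
- **More blanks in controls is unproven.** A reader might infer from Protocol 9.1.2 that the field will be left empty in controls and that a real excess will be masked or reversed. That sentence omits INTELLiVENT-ASV for both arms, SAP 8.5 offers a not-related category for SAEs, and the case report form is not among the documents.
- **Safeguards exist.** The eCRF generates queries (Protocol 11.2.1), events are screened twice a day (9.3), and the medical monitor reviews each one (1.6). Listings by arm flag related events (SAP 8.5), though nothing says imputed ratings will be marked.

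None of this makes the imputed value correct for an unexposed subject. The safeguards should make it rare; they do not change the rule that applies when it happens.

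**Conclusion.** The rule is wrong as written, within a limited scope. For an unexposed control it replaces a known answer with a false one, in descriptive outputs presented by arm. If missingness is small and equal, the loss is p(1 - m) against p: for a true 5-point excess, 4.9 points at 2% missing, 4.75 at 5%, 4.5 at 10% and 4.0 at 20%, together with the loss of a clean zero in the control column. Masking or reversal is arithmetically possible only with higher missingness in controls. The threshold ranges from 6.9% to 52.5% in the cases above, and the documents give no rate to place the trial on that range. These figures rest on assumed AE, relatedness and missingness rates, equal AE shares in the two arms, and missingness unrelated to true relatedness.

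A separate gap limits how far the effect can be traced. SAP 8.5 defines related events by a list that contains both 'Not related' and 'Related', while SAEs are graded on four causality levels. How an imputed possibly related enters the ADE and SADE counts is therefore not stated.

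**What to change.** 1. **SAP 4.8.** Apply the possibly-related imputation for the investigational device only to AEs in subjects who received INTELLiVENT-ASV, with onset at or after its start. Otherwise code the INTELLiVENT-ASV relationship as not applicable. In exposed subjects, treat an onset that cannot be placed as on or after the start, because SAP 4.7 moves a missing start day to the first of the month and could put it wrongly before exposure.
2. **SAP 4.8.** Impute a missing relationship to mechanical ventilation or study procedure by the same rule in both arms, so that genuine comparator- and procedure-related events are kept.
3. **SAP 8.5.** Show INTELLiVENT-ASV relationship tables for exposed subjects only, and report the number of imputed ratings by arm.
4. **SAP 8.5.** Correct the definition of related AEs and state which causality levels, including possibly related, count toward ADE and SADE.

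The cost is a few sentences in the SAP and one programming condition. No new data are needed, and no endpoint, alpha or sample size changes.
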